In Phase II, for participants randomized to the treatment arm, if the participant does not complete the post-intervention assessments within 2 weeks from the end of the intervention period they will be considered lost to follow up. If a participant chooses to withdraw from the study at any point or the participant is deemed lost to follow up or is dropped from the study during the intervention period (5 weeks), access to the web portal and mobile app will be restricted at that time, otherwise access to the mobile app will be restricted at the end of the intervention period and access to the web portal will be restricted after post-intervention assessments have been completed or the participant is deemed lost to follow up (2 weeks after intervention period).

Participants randomized to the control arm will have two weeks to complete the post-intervention assessments. Once the post-intervention assessments have been completed or 2 weeks have passed, whichever occurs first, participants in the control arm will be granted access to the treatment condition (Limbix Spark) for 5 weeks. After access to Limbix Spark for 5 weeks, participants will have two weeks to complete another set of post-intervention assessments. If a participant chooses to withdraw from the study or the participant is deemed lost to follow up during the control app intervention period or Limbix Spark app intervention period (5 weeks

each), access to the web portal and mobile app will be restricted at that time. Otherwise, access to the mobile app will be restricted at the end of each intervention period and access to the web portal will be restricted after the second set of post-intervention assessments have been completed or the participant is deemed lost to follow up (2 weeks after Limbix Spark intervention period).

In Phase II, if participants report a change in their treatment for a mental health disorder while enrolled in the study, they may be withdrawn from the study.

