### **3.4 Assessments**

Baseline and post-intervention assessments for participants and parents (if under 18) will be completed via a secure web portal. Weekly participant assessments will be completed in the mobile app. Weekly parent assessments will be completed via secure web portal.

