###### Phase II

- Remission rates based on PHQ-8 < 10
- Between-group treatment-related differences in participant-rated anxiety symptoms and global functioning as measured by GAD-7 and PROMIS Pediatric Global Health Scale
- Between-group treatment-related differences in parent-reported depressive symptoms and global functioning as measured by MFQ, and PROMIS Parent Proxy Global Health Scale
- Average treatment-related usability (SUS) and engagement (UES-SF) ratings
- Between-group treatment-related differences in clinical concern rates and serious clinical concerns
- Between-group treatment-related differences in program adherence and engagement based on behavioral and mobile app analytics
- 

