## Phase II

The main purpose of Phase II is to evaluate the effectiveness of the Limbix Spark program relative to an educational control condition. All analyses will be restricted to those participants with PHQ-8  $\geq 10$  unless otherwise indicated. Data from participants who reported a change in their medication or treatment for a mental health disorder that occurred during the study may be excluded from primary analysis. The core analysis strategy in this project is longitudinal mixed effects modeling, where we fully utilize the repeatedly measured primary and secondary outcomes and maximum likelihood estimation will be applied.

Data across versions 2 and 3 will be pooled and statistical analyses conducted with the combined dataset may be computed with version included as a covariate. Statistical analyses may also be conducted separately for versions 2 and 3 cohorts. All analyses will be completed in line with the intent-to-treat (ITT) principle, where all participants will be included in the analyses according to their assigned study arm at baseline, regardless of adherence to study protocol. Modern per protocol analyses will also be conducted to estimate treatment effects for participants who adhered to the protocol. All analysis results will be two-tailed, with a significance level at 0.05 and 95% confidence intervals.

All measures will be analyzed using mixed effects modeling, followed by generalized estimating equations to account for irregularly spaced measurements, fully utilizing all repeated measures and all available data. Missing data will be imputed using multiple imputation and likelihood-based analyses. Case analysis or single

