#### **4.5 Data Monitoring**

This is a low risk research study.

A clinical concern is defined here as any negative experience or symptom reported by participant or parent in the Participant Symptom Check Questionnaire, in freeform text, spontaneously reported, or clinically significant deterioration of symptoms, whether or not thought to be associated with participation in the study.

Clinical concerns will be categorized as follows:

0- Not a clinical concern: Research team determined that triggering event was not a clinical concern

1- Mild clinical concern: Research team determined that triggering event doesn't require clinician input and will continue to monitor participant's responses

2- Moderate clinical concern: Research team determined that triggering event requires clinician input. Clinician determined that research team should continue to monitor participant's responses but that no follow-up was needed.

3- Elevated clinical concern: Research team determined that triggering event requires clinician input. Clinician determined follow-up was indicated and confirmed participant safety (participant did not endorse intent to self harm) via email or phone communication with participant or their parent/guardian or their provider.

4- Significant clinical concern: Research team determined that triggering event requires clinician input. Clinician determined that follow-up was indicated and after follow-up with participant, parent/guardian, or provider determined that participant should be withdrawn from study (e.g. due to suicide attempt, self-harm or self-harm attempt, suicidal ideation with intent, reported hospitalization for self-harm or suicide attempt while enrolled in study).

All adverse device effects and complaints will be recorded (whether anticipated or unanticipated). The project PI and study clinician will determine whether it is in the participant's best interest to remain in the study after any clinical concern.

Anticipated serious clinical concerns, given the study population, include depressive symptoms as defined in the DSM-V, suicidal ideation, active self-harm, clinically significant deterioration in depressive symptoms, suicide attempts, and suicide.

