### **7.3 Protection Against Risk**

To minimize psychological risks, participants will be instructed that they can choose not to answer any question in any assessment and can discontinue their participation at any time. As the mobile app progresses in a linear fashion, questions in the mobile program must be answered to progress to the next task. During consent, participants will be informed that if they do not wish to answer a question in the mobile app they may discontinue their participation at any time. Patient responses to assessments completed weekly will be monitored as well as free response answers to questions delivered via the mobile app. This will enable detection of deterioration in clinical status. If such deterioration occurs, research staff will immediately contact the PI/study clinician. Participation will be terminated if clinical evidence indicates that continuing would not be in the best interest of the subject as determined by study PI in consultation with a study clinician. Weekly symptom reporting will also help the research team to identify any psychological or physical health consequences of study participation and, in consultation with study clinicians, determine the best way to mitigate further risks to participant health.

To minimize risks to privacy and/or confidentiality, only personnel with training in protecting private information about human subjects will have access to study data. Special care will be taken to prevent unauthorized access to data files.

Computers on which data files will be accessed will have password-protected access. All study participants will be assigned code numbers on entry to the study and all subsequent data processing will be completed by reference to these numbers. Special care will be taken to prevent unauthorized access to the data file connecting participant identity to subject numbers.

All publications or reports of data will be anonymous in relation to subject identification. Protected health information will be disclosed to other professionals treating the patient only upon written authorization of the patient. PIs will retain responsibility for ensuring that files are maintained in a secure manner during and after study.

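### Phase II remission has no rule for participants removed on clinical grounds, so by default such a participant can be imputed as a remitter or leave the denominator

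*Combined protocol and SAP*

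**What the plan says.** - **Removal on clinical grounds.** Section 7.3: "Participation will be terminated if clinical evidence indicates that continuing would not be in the best interest of the subject". The judgement is the PI's, in consultation with a study clinician. Section 4.5 defines category 4 as the case where the clinician "determined that participant should be withdrawn from study (e.g. due to suicide attempt, self-harm or self-harm attempt, suicidal ideation with intent", among other examples.
- **Access after removal.** For the Phase II treatment arm, section 3.1 names withdrawal and loss to follow-up, and adds a third case: "dropped from the study during the intervention period (5 weeks), access to the web portal and mobile app will be restricted at that time". The parallel control-arm sentence begins "If a participant chooses to withdraw from the study or the participant is deemed lost to follow up during the control app intervention period" and does not mention participants who are dropped.
- **Where the endpoint is collected.** Section 3.4: "Baseline and post-intervention assessments for participants and parents (if under 18) will be completed via a secure web portal". No section plans to collect outcomes after removal.
- **Endpoint.** Section 4.2 lists first among the Phase II secondary outcomes: "Remission rates based on PHQ-8 < 10". Section 3.4 defines remission by the post-intervention score alone.
- **Missing data.** Section 4.4, Phase II: "Missing data will be imputed using multiple imputation and likelihood-based analyses". It also allows case analysis or single imputation, with the approach selected once the data are in hand. Analyses follow intent-to-treat and use all repeated measures. No sentence distinguishes removal on clinical grounds from other missingness.

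**The concern.** A participant whom the study team removes because of clinical deterioration is not an ordinary dropout. The reason for the missing score is known, and it bears directly on the outcome. The plan nevertheless gives remission no rule for this case, and the two main routes it offers both lean the same way within an arm. Imputation gives the participant some chance of a score below 10. Case analysis takes the participant out of the denominator. Under neither does the removal itself count against remission.

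At stake is the remission rate in each arm and the difference between them. Readers are likely to take up a remission rate readily, and a report that counted someone withdrawn after a suicide attempt as remitted would be hard to defend.

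**Working it through.** **The plan's own figures.** The plan gives no figure on this point. Its one computable design figure is the total of 175 in section 2.1: a two-sample t-test at d = 0.5, 80% power and two-sided 0.05 needs 64 per arm, and 128/0.73 = 175.3. It reproduces, and nothing below depends on it beyond arm size. The Phase II minimum of 120 gives 60 per arm; 175 gives about 87. One reclassified participant moves an arm's rate by 1/60 = 1.67 points or 1/87 = 1.15 points.

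**Step 1: can a removed participant be imputed below 10?** Let L be the last weekly PHQ-8, f the further fall the imputation model expects, and s the residual SD. With a cut at 9.5,

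P(imputed < 10) = Φ((9.5 − (L − f))/s).

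Assumed ranges: f from 0 to 4 points, s from 3 to 5.

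| Last score L | Lowest | Highest |
|---|---|---|
| 12 | 0.20 (f 0, s 3) | 0.69 (f 4, s 3) |
| 14 | 0.07 (f 0, s 3) | 0.46 (f 4, s 5) |
| 18 | 0.002 (f 0, s 3) | 0.18 (f 4, s 5) |
| 24 | about 0 | 0.02 (f 4, s 5) |

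So it is unlikely after a high last score and not negligible after a moderate one.

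**Step 2: arm-level probabilities.** Assumed: baseline mean 14.5 (SD 3.2, restricted to 10 or more), mean 5-week change −4.5 on Spark and −2.5 on control, termination after week 2, imputation by arm from baseline and weeks 1 and 2. A simulation of 400 trials per scenario gave a terminated participant a chance of being imputed as a remitter of about 17–43% on Spark (p_S) and 10–28% on control (p_C). The low ends assume a visible 5-point worsening before termination, the high ends none.

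The high ends can be checked by hand, since with no visible worsening the imputed score follows the arm's own week-5 distribution:

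- Spark mean 14.5 − 4.5 = 10.0, giving Φ(−0.5/3) = 0.43 to Φ(−0.5/5) = 0.46.
- Control mean 14.5 − 2.5 = 12.0, giving Φ(−2.5/3) = 0.20 to Φ(−2.5/5) = 0.31.

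**Step 3: shift in the between-arm difference.** With termination rates t_S and t_C, and counting terminated participants as non-remitters as the reference,

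shift = t_S·p_S − t_C·p_C.

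| Terminated, Spark / control | Low end (points) | High end (points) |
|---|---|---|
| 5% / 5% | 5 × (0.17 − 0.10) = 0.35 | 5 × (0.43 − 0.28) = 0.75 |
| 8% / 2% | 8 × 0.17 − 2 × 0.10 = 1.2 | 8 × 0.43 − 2 × 0.28 = 2.9 |
| 2% / 8% | 2 × 0.17 − 8 × 0.10 = −0.5 | 2 × 0.43 − 8 × 0.28 = −1.4 |

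The simulation agrees closely: 0.4–0.7 points for the first row and 1.1–2.8 for the second.

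**Step 4: direction.** The shift is zero when t_C/t_S = p_S/p_C, that is 0.43/0.28 = 1.5 or 0.17/0.10 = 1.7. Under these inputs the difference is inflated in Spark's favour unless the control rate is more than about 1.5 to 1.7 times the Spark rate.

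**Step 5: case analysis.** If an arm's remission rate among those with a score is r, dropping a share t reports r where the reference is r(1 − t), an excess of r·t. With r equal to the assumed arm rates of 0.43 and 0.28, this equals the high-end column above.

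**The case against.** The strongest reply is that the plan leaves the scoring open; it does not commit to a bad rule. Imputation is the default, but case analysis and single imputation are allowed, and participants whose treatment changed may be excluded from the primary analysis. Section 4.4 never says remission will be derived from imputed scores, and it treats every variable except clinical concerns as continuous. The participant's own weekly scores before removal also enter the model, so a recorded deterioration makes an imputed remission unlikely. That all stands, and it limits the claim to what the default permits. It does not close the gap: no permitted route carries a rule that counts such a participant as not in remission. Sections 4.5 and 4.5.1 also take concerns from symptom checks, free text and correspondence, so a category 4 event need not follow a high PHQ-8.

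Second, scoring removal as non-remission is a choice of endpoint, and the rates are overstated only relative to that choice. This is fair. It is, however, a standard choice for a responder endpoint, and the plan states no alternative.

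Third, the events are not hidden. Section 4.2 compares serious clinical concerns between groups, and the DSMB reviews all clinical concerns quarterly. Section 2.6 also excludes a lifetime suicide attempt, active self-harm and ideation with intent, which should keep numbers low. This limits the consequences but does not correct the remission rate.

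A reader might also infer that both arms lose the post-intervention score. For dropped participants, section 3.1 says so only for the treatment arm. Nor does section 7.3 itself mention a suicide attempt; that example is in category 4 of section 4.5.

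**Conclusion.** The point holds in a limited form, at minor severity. By default, a participant removed on clinical grounds can be imputed as a remitter or leave the denominator.

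The size is small: under 1 point on the between-arm difference at equal 5% termination rates, about 1 to 3 points inflation at 8% against 2%, and about 0.5 to 1.4 points understatement at 2% against 8%. Every PHQ-8 and termination input is an assumption, and nothing in the documents supports an imbalance in either direction. For scale, at 60 per arm and an assumed 30% remission, the standard error of the difference is √(2 × 0.30 × 0.70/60) = 8.4 points.

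Two stronger readings are tempting. One is that a participant withdrawn after a suicide attempt will be counted as remitted; the documents support only that the default allows it. The other is that the bias favours whichever arm loses more deteriorating participants; the equal-rate result contradicts this, because the direction depends on both the termination rates and how favourable each arm's imputations are.

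**What to change.** Add to section 4.4, Phase II, for remission:

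> A participant whose participation is ended by the study team on clinical grounds under 7.3, or who is withdrawn with a category 4 clinical concern, before the first post-intervention assessment and who has no PHQ-8 from that assessment is counted as not in remission, in both arms. Multiple imputation for remission applies only to other missing scores.

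Then:

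- Record the reason for every study-team termination. A termination under 7.3 need not be graded category 4, so the grading alone does not identify these participants.
- Report these terminations by arm beside the remission rates.
- Reconcile the treatment-arm and control-arm wording on portal access in section 3.1, so that the rule meets the same kind of missing score in both arms.

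The cost is two sentences, one recorded field and slightly lower reported remission rates. The change concerns analysis only and leaves the criteria for ending participation as they are. It does not reach participants who deteriorate and drop out without being removed; their scores would still be imputed.

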#### **7.4 Potential Benefits to the Subjects**

No direct benefits can be guaranteed by participating in this research protocol. As participants in the treatment arm will receive a mobile program designed to be therapeutic they may experience direct benefits from participation in terms of reduced symptoms of depression, as well as potential reductions in comorbid anxiety symptoms, and improvements in mood, and/or functional outcomes. Participants in the control arm will receive educational information about depression, including information on healthy habits and wellbeing which may also result in direct benefits from participation in terms of reduced symptoms of depression, as well as potential reductions in comorbid anxiety symptoms, and improvements in mood, and/or functional outcomes.

Participants may also directly benefit from participating in the proposed research because of the knowledge obtained. Assessments and procedures completed during the study may provide participants with an opportunity to reflect on their thoughts, feelings, and behaviors which may be valuable in helping individuals better understand their own emotional functioning. These benefits outweigh the minimal risks associated with this trial.

Participants will have the opportunity to provide feedback about the intervention to help improve the program for future users. This ability to help others may also have therapeutic benefits for participants.

#### **7.5 Alternatives to Participation**

Prospective participants who decline to enroll in this study are free to consider alternatives, including seeking treatment. Standard of care treatment for adolescent depression typically includes psychotherapy with or without antidepressants, depending on clinically determined variables. Mental health resources will be shared with potential participants who decline to participate in this study but are treatment-seeking. However, alternative treatments are not promised or guaranteed.

### **8. Subject Identification, Recruitment and Consent/Assent**

#### **8.1 Method of Subject Identification and Recruitment**

Participants will be recruited via online advertising, social media, word of mouth, flyers, and recommendations by doctors, schools, and other youth and health focused organizations. Providers may be compensated for recruitment efforts (based on hourly effort and not on number of referrals or enrolled participants). Online ads will be targeted to adolescents ages 13-21 or to the parents of adolescents nationwide. Study ads will direct potential participants to a study landing page. The study landing page will provide a basic overview of the study and will ask interested participants to confirm their eligibility based on provided eligibility criteria and set up a virtual consent appointment with a research coordinator. Interested potential participants under 18, when required, will be instructed that they will need a legal guardian to attend the virtual consent appointment.

Flyers and advertisements (provided as attachments) may also be posted online on Craigslist, Facebook, and other websites.

## **8.2 Process of Consent**

Any trained member of the research team will be authorized to obtain informed consent.

Prior to participation, e-consent will be obtained for all participants over 18. For participants under 18, e-consent from a legal guardian and documented assent from participants will be obtained.

The consent process will be completed virtually via videoconferencing. To ensure participant privacy, the research staff member conducting the consent process will ensure that no one outside of the research team can overhear the consent process from their end and will recommend that the potential participant join the videoconference from a private location.

The researcher will explain the study, review the consent form, take time to answer any questions, provide time for decision-making and request an electronic signature.

The session will emphasize:

- 1) This is a research study testing an investigational medical device intended as a treatment for depression
- 2) Possible (minimal) risks and benefits of participation,
- 3) Participants can elect not to respond to any question(s) they are not comfortable answering
- 4) Participants can choose to end their participation at any time for any reason
- 5) All information will be kept confidential with the exception of certain information we must report for legal or ethical reasons including suspected child abuse or neglect, suspected elder abuse or neglect, or intent to harm oneself or others.

The consent and assent process will be considered complete only if the adolescent (and legal guardian if the participant is under 18) report comfort with and comprehension of all study procedures. The session will proceed only if informed consent is obtained.

After all questions concerning any aspect of the study have been fully answered by study staff, a Part 11 compliant, electronic signature (via HelloSign) will be obtained from the participant or their legal guardian (if under 18) to document consent. Documentation of the assent of a minor will also be obtained. Participants or their legal guardian will be required to display a valid form of identification to verify identity. Participants will be provided with a link to access and download a copy of the signed consent form at any time. Signed electronic consent forms will be stored through HelloSign Part 11 compliant services.

If a minor will become of legal consenting age during their participation in the study they will be required to set up an e-consent appointment at that time and consent to continuing their participation.

